Subjects will begin dosing at 100 mg on Lead-in Day 1 (LD1). This is the dose level at which a mean maximal platelet drop of approximately 60% from baseline with recovery during 14 days of dosing is expected based on observations in this study to date. The lead-in titration dose may be adjusted if the defined dose level fails to significantly mitigate ABT-263-induced thrombocytopenia following the lead-in period or the defined dose level results in significant occurrence of DLT in the lead-in period.

A subject may only proceed from the lead-in period to the defined dose level for Cycle 1 Day 1 and beyond if platelet count is $\geq 50,000/\text{mm}^3$ after Lead-in Day 7 and stable or increasing. If the platelet count is $< 50,000/\text{mm}^3$ after Lead-in Day 7, the visit day will be considered Lead-in Day 8 and the subject will continue to receive the lead-in dose until the platelet count is $\geq 50,000/\text{mm}^3$.

When the platelet count is $\geq 50,000/\text{mm}^3$, the subject will receive the lead-in dose that day, and the next day (defined as Cycle 1 Day 1) the subject will receive the defined dose for Cycle 1 Day 1, provided the pre-dose platelet count that day is $\geq 50,000/\text{mm}^3$ and platelets are stable or increasing. For example, if a subject's platelet count is $\geq 50,000/\text{mm}^3$ on Lead-in Day 9, the subject will take the lead-in dose on Day 9. The next day will be considered Cycle 1 Day 1 and the subject will begin receiving the defined dose for Cycle 1 Day 1. However, if the pre-dose platelet count is $< 50,000/\text{mm}^3$ or

[figure not shown]
platelets are decreasing, then the day becomes Lead-in Day 10 and the subject continues dosing at the lead-in dose.

If the platelet count is $< 50,000/\text{mm}^3$ after 14 days at the lead in dose, the lead in dose will become the subject's dose for the duration of the study. To change from the lead in dose to a higher dose (for subjects who continue receiving the lead in dose beyond the lead in period), a discussion between the investigator and the AbbVie Medical Monitor is required.

The period for defining DLTs will be the total days dosed in the lead-in period plus 21 days dosed in Cycle 1 (28 days if subject moves to Cycle 1 Day 1 after the planned 7 day lead-in period).

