6.7.2 Management of Thrombocytopenia

ABT-263 induces apoptosis, rather than lysis, of circulating platelets, which differs from typical chemotherapy induced thrombocytopenia related to myelosuppression.

All decisions regarding continued ABT-263 dosing for individual subjects will be determined by the investigator, in conjunction with the AbbVie Medical Monitor, as appropriate. These decisions should be guided by the following:

Administration of ABT-263 will be interrupted or discontinued for:

- Any pre-dose platelet count $< 25,000/\text{mm}^3$
- Any clinically significant bleeding, defined as Grade 2 or higher hemorrhage

If ABT-263 is held, it may be restarted, but only at a reduced dose to be jointly defined by the investigator and the AbbVie Medical Monitor, once the subject's platelet count is $\geq 50,000/\text{mm}^3$. The dose may be increased (not to exceed the highest tolerated dose) thereafter upon joint determination of the AbbVie Medical Monitor and the investigator.

After any Grade 4 platelet count $< 25,000/\text{mm}^3$ is observed for the first time in a subject, serial PK samples will be collected. PK samples will be collected as soon as possible after the Grade 4 platelet count is determined and then 24 and 48 hours after the event. Starting with Protocol Amendment 13, PK samples will NOT be collected.

Limited human clinical data are available to understand the response to infusion of exogenous platelets in the presence of circulating drug levels. Platelet transfusion studies conducted in beagle dogs demonstrated that transfusion of one-day old platelets administered near the time of ABT-263 C_{max} , resulted in higher platelet levels than dogs not receiving supplemental platelets. Platelet concentrations remained higher after 24 hours with declining ABT-263 concentrations. This study suggests that infusion of

platelets may have beneficial effects in treating acute thrombocytopenia following oral dosing with ABT-263.

If platelet transfusions are required in response to active bleeding, dosing of ABT-263 should be suspended. It should be noted that platelet response with transfusions may not follow typical platelet kinetics of thrombocytopenia as with typical chemotherapy induced myelosuppression. Procedures consistent with local institutional blood banking guidelines regarding platelet transfusions should be followed.

Platelet Transfusion Recommendations:

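### Section 5.1's lead-in platelet rule has no lower limit, so below 25,000/mm³ it disagrees with Section 6.7, chiefly over the first dosing after recovery

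*Protocol*

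**What the plan says.** The lead-in text appears twice in Protocol Section 5.1, once for the Phase 1 21/21 schedule and once for Phase 2a, in nearly the same words. Subjects start at 100 mg. If the count is below 50,000/mm³ after Lead-in Day 7, "the subject will continue to receive the lead-in dose until the platelet count is" at least 50,000/mm³. On the day it reaches that level the lead-in dose is given, and "the next day (defined as Cycle 1 Day 1) the subject will receive the defined dose for Cycle 1 Day 1", provided the pre-dose count is again at least 50,000/mm³ and platelets are steady or rising. The defined dose is 250 mg in Phase 2a. The completed Phase 1 21/21 levels listed in Section 3.0 are 125, 200, 250 and 300 mg.

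Section 6.7.2 says: "Administration of ABT-263 will be interrupted or discontinued for" any pre-dose count below 25,000/mm³. It continues: "If ABT-263 is held, it may be restarted, but only at a reduced dose to be jointly defined" by the investigator and Medical Monitor, once the count is at least 50,000/mm³. Any later increase is again a joint decision. Section 6.7.1 classes a drug-related count below 25,000/mm³ as a DLT unless a same-day repeat is 25,000/mm³ or more. It requires interruption after any DLT, and reintroduction at a reduced dose.

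**The concern.** Both rules act on the platelet count that the investigator reviews before dosing. A count of 20,000/mm³ on Lead-in Day 9, for example, meets the Section 5.1 condition for continuing 100 mg and the Section 6.7.2 condition for stopping. When the count recovers, both rules respond at the same threshold of 50,000/mm³: one raises the dose and the other permits only a reduced one. The lead-in paragraphs do not refer to Section 6.7, Section 6.7 does not exempt the lead-in, and neither states which takes precedence. A reader who lets a specific rule override a general one would follow Section 5.1, the less cautious of the two. What is at stake is a dosing instruction on the expected dose-limiting toxicity.

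**Working it through.** No sample-size or error-rate figure is involved, so the check is a comparison of the two rules followed by simple arithmetic.

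**Step 1. The rules side by side, after Lead-in Day 7**

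| Situation | Section 5.1 | Sections 6.7.1 and 6.7.2 | Consistent? |
|---|---|---|---|
| 25,000 to below 50,000 | Continue 100 mg | No hold on platelet count | Yes |
| Pre-dose count below 25,000 | Continue 100 mg | Interrupt or discontinue | No, as written |
| First day at 50,000 or more after such a count | 100 mg | Reduced dose only, set jointly | No, if reduced means below 100 mg |
| Next day, still at least 50,000 and steady or rising | Defined dose | Increase only by joint decision | No |

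Section 6.7 does not name the dose from which the reduction is made. The natural reading is the dose that was held, 100 mg. Doses below 100 mg can be made up, since Section 5.5.2 lists 25 mg tablets. If the reduction were instead taken from the defined dose, 100 mg on the recovery day could pass. The automatic step-up on the following day would still conflict.

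**Step 2. Size of the dose difference after recovery**

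Ratio = defined dose / lead-in dose.
- Phase 2a: 250/100 = 2.5.
- Phase 1 21/21 levels: 125/100 = 1.25 up to 300/100 = 3.0.

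Under Section 6.7 the corresponding ratio at restart is below 1 on the natural reading.

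**Step 3. How easily the case arises**

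Inputs: the entry minimum is 75,000/mm³ (Sections 5.2.1 and 5.2.3), and Section 5.1 expects "a mean maximal platelet drop of approximately 60% from baseline" at 100 mg. The assumption is that the Lead-in Day 1 count equals the baseline shown.
- Count after a 60% drop from the entry minimum: 75,000 × (1 − 0.60) = 30,000, which is above 25,000.
- Baseline at which a 60% drop gives 25,000: 25,000/0.40 = 62,500, which is below the entry minimum.
- Drop needed to reach 25,000 = 1 − 25,000/baseline. This is 66.7% from 75,000, 75% from 100,000 and 83.3% from 150,000. Falling below 25,000 takes more than that.

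An average responder therefore stays out of the conflict band. Because 60% is a mean, some individual drops are larger, but the documents give no spread. The count must also be that low after Day 7, or dosing must be restarting after such a count, whereas Section 3.0 says nadirs typically come in the first few days.

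**Step 4. Effect on DLT scoring**

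Section 8.1.1 scores each subject 0 or 1. A drug-related count below 25,000/mm³ that a same-day repeat has not overturned is already a DLT under Section 6.7.1, so the dose given afterwards does not change that score.

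**The case against.** The strongest reply is that Section 6.7 already covers this. Section 6.7.2 applies to any pre-dose count and opens with a general statement: "All decisions regarding continued ABT-263 dosing for individual subjects will be" determined by the investigator with the Medical Monitor. Section 5.1 itself brings the Phase 1 lead-in under the DLT rules: "The period for defining DLTs will be the total days dosed in the lead-in period" plus the 21 days of Cycle 1. The platelet procedures in Section 5.3.1.1 require daily counts when the lead-in runs past Day 7, review before dosing, and same-day confirmation below 25,000/mm³. They also refer to holds under Sections 6.7.1 and 6.7.2. On this view 50,000 is the gate for stepping up, 25,000 is the trigger for stopping, and the continuation sentence only says which dose level applies.

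Most of that stands, and it makes a hold the likely practice. A reader might infer that the protocol directs sites to dose through Grade 4 thrombocytopenia; taken as a whole, the documents do not support this. The reply does not settle the recovery sentence, which gives 100 mg and then the defined dose with no mention of a joint decision.

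A reader might also place the 14-day sentence, which makes the lead-in dose permanent, in the same conflict. It only assigns a dose level, and for any later increase "a discussion between the investigator and the AbbVie Medical Monitor is required".

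Finally, a reader might expect corrected wording to help interpret lead-in dosing records already collected. It cannot change what sites were told at the time. The SAP reports 29 Phase 1 and 31 Phase 2 subjects already treated, and the documents show no further lead-in dosing planned.

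**Conclusion.** The point holds as a minor, narrow inconsistency. Both lead-in paragraphs are wrong as written for pre-dose counts below 25,000/mm³. Section 6.7 most likely governs the hold, so the main unresolved conflict is the first dosing after recovery: up to 250 mg in Phase 2a (2.5 times the lead-in dose), or 1.25 to 3.0 times at the Phase 1 21/21 levels, against a reduced dose under Section 6.7. That contrast assumes a site follows Section 5.1 at recovery and that a reduced dose means one below 100 mg. If the reduction is measured from the defined dose, only the next-day step-up conflicts. The number of subjects affected cannot be computed. A reader might infer a bias in the DLT rate or the MTD; DLT counting, the MTD and all analyses are unaffected.

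**What to change.** In both lead-in paragraphs of Section 5.1 (Phase 1 21/21 and Phase 2a), limit the continue-dosing rule to counts of 25,000 to below 50,000/mm³ and add:

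> For any pre-dose count below 25,000/mm³ during the lead-in (with same-day confirmation per Section 6.7.1), Sections 6.7.1 and 6.7.2 govern: ABT-263 is interrupted or discontinued, may be restarted only at a jointly defined reduced dose once the count is at least 50,000/mm³, and there is no automatic move to the Cycle 1 Day 1 dose. Any later increase is by joint decision of the investigator and Medical Monitor.

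The cost is one range limit and one short insertion in each of two places, with no new data, procedures or analyses. The benefit is a consistent safety instruction.

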5.2 Selection of Study Population

Subjects will undergo screening procedures within 14 days prior to initial study drug administration (Lead-in Day 1/Cycle 1 Day 1). Adult male and female subjects with CLL who meet the inclusion criteria and who do not meet any of the exclusion criteria will be eligible for enrollment into the study.

5.2.1 Phase 1 Inclusion Criteria

A subject will be eligible for study participation if he/she meets the following criteria:

1. The subject must be ≥ 18 years of age.
2. The subject must have relapsed or refractory CLL and require treatment in the opinion of the investigator.
3. The subject has an Eastern Cooperative Oncology Group performance score of ≤ 1 .
4. Subjects receiving Selective Serotonin Reuptake Inhibitor (SSRI) anti-depressants (e.g., Prozac) must be receiving a stable dose for at least 21 days prior to the first dose of study drug.
5. The subject must have adequate bone marrow independent of growth factor support (with the exception of subjects with ANC $< 1000/\mu\text{L}$ and bone marrow heavily infiltrated with underlying disease [80% or more]), renal and hepatic function, per local laboratory reference range at Screening as follows:
 - Bone marrow: Absolute Neutrophil count (ANC) $\geq 1000/\mu\text{L}$;
Platelets $\geq 75,000/\text{mm}^3$ (entry platelet count must be independent of transfusion within 14 days of Screening), Hemoglobin $\geq 9.0 \text{ g/dL}$;
 - Renal function: Serum creatinine $\leq 2.0 \text{ mg/dL}$ or calculated creatinine clearance $\geq 50 \text{ mL/min}$;
 - Hepatic function and enzymes: AST and ALT $\leq 3.0 \times$ the upper normal limit (ULN) of institution's normal range; Bilirubin $\leq 1.5 \times$ ULN. Subjects with Gilbert's Syndrome may have a Bilirubin $> 1.5 \times$ ULN;
 - Coagulation: aPTT, PT, not to exceed $1.2 \times$ ULN.
6. Female subjects must be surgically sterile, postmenopausal (for at least 1 year), or have negative results for a pregnancy test performed as follows:
 - At Screening on a serum sample obtained within 14 days prior to initial study drug administration, and

- Prior to dosing on a urine sample obtained on Cycle 1 Day 1 or Lead-in Day 1 (lead-in period) if it has been > 7 days since obtaining the serum pregnancy test results.
7. All female subjects not surgically sterile or postmenopausal (for at least 1 year) and non-vasectomized male subjects must practice at least one of the following methods of birth control:
- total abstinence from sexual intercourse (minimum one complete menstrual cycle);
 - a vasectomized partner;
 - hormonal contraceptives (oral, parenteral or transdermal) for at least 3 months prior to study drug administration;
 - double-barrier method (including condoms, contraceptive sponge, diaphragm or vaginal ring with spermicidal jellies or cream).
8. The subject must voluntarily sign and date an informed consent, approved by an Independent Ethics Committee (IEC)/Institutional Review Board (IRB), prior to the initiation of any screening or study-specific procedures.

5.2.2 Phase 1 Exclusion Criteria

A subject will not be eligible for study participation if he/she meets any of the following criteria:

1. The subject has a history or is clinically suspicious for cancer-related Central Nervous System (CNS) disease.
2. The subject has undergone an allogeneic or autologous stem cell transplant.
3. The subject has a recent history (within 1 year prior to first dose of study drug) of an underlying, predisposing condition of bleeding or currently exhibits signs of bleeding.
4. The subject has active peptic ulcer disease or other potentially hemorrhagic esophagitis/gastritis.

5. The subject has active immune thrombocytopenic purpura or a history of being refractory to platelet transfusions (within 1 year prior to the first dose of study drug).
6. The subject has received aspirin within 7 days prior to the first dose of study drug.
7. The subject is currently receiving or requires anticoagulation therapy or any drugs or herbal supplements that affect platelet function, with the exception of low-dose anticoagulation medications that are used to maintain the patency of a central intravenous catheter.
8. Subject has received steroid therapy for anti-neoplastic intent within 7 days prior to the first dose of study drug with the exception of inhaled steroids for asthma, topical steroids, or replacement/stress corticosteroids.
9. The subject has received any anti-cancer therapy including chemotherapy, immunotherapy, radiotherapy, hormonal (with the exception of hormones for thyroid conditions or estrogen replacement therapy [ERT]), or any investigational therapy within 14 days prior to the first dose of study drug, or has not recovered to less than grade 2 clinically significant adverse effect(s)/toxicity(ies) of the previous therapy.
10. The subject has received a biologic within 30 days prior to the first dose of study drug.
11. The subject has consumed grapefruit or grapefruit products within 3 days prior to the first dose of study drug.
12. The subject has a significant history of cardiovascular disease (e.g., myocardial infarction [MI], thrombotic, or thromboembolic event in the last 6 months), renal, neurologic, psychiatric, endocrinologic, metabolic, immunologic, or hepatic disease that in the opinion of the investigator would adversely affect his/her participating in this study.
13. A female subject is pregnant or breast-feeding.

14. The subject has tested positive for HIV (due to potential drug-drug interactions between anti-retroviral medications and ABT-263, as well as anticipated ABT-263 mechanism based lymphopenia that may potentially increase the risk of opportunistic infections and potential drug-drug interactions with certain anti-infective agents).
15. The subject has a history of other active malignancies within the past 3 years prior to study entry, with the exception of:
 - adequately treated *in situ* carcinoma of the cervix uteri;
 - basal or squamous cell carcinoma of the skin;
 - previous malignancy confined and surgically resected with curative intent.
16. The subject exhibits evidence of other clinically significant uncontrolled condition(s) including, but not limited to:
 - Uncontrolled systemic infection (viral, bacterial, or fungal)
 - diagnosis of fever and neutropenia within 1 week prior to study drug administration.

5.2.3 Phase 2a Inclusion Criteria

A subject will be eligible for study participation if he/she meets the following criteria:

1. The subject must be ≥ 18 years of age.
2. The subject must have CLL and require treatment in the opinion of the investigator.
3. The subject has relapsed disease and has received no more than 5 prior myelosuppressive/chemotherapy regimens.
4. Subject has an Eastern Cooperative Oncology Group performance score of ≤ 1 .
5. Subjects receiving Selective Serotonin Reuptake Inhibitor (SSRI) anti-depressants (e.g., Prozac) must be receiving a stable dose for at least 21 days prior to the first dose of study drug.

6. The subject must have adequate bone marrow independent of growth factor support (with the exception of subjects with ANC < 1000/ μ L and bone marrow heavily infiltrated with underlying disease [80% or more]), renal and hepatic function, per local laboratory reference range at Screening as follows:
 - Bone marrow: Absolute Neutrophil count (ANC) \geq 1000/ μ L; Platelets \geq 75,000/ mm^3 (entry platelet count must be independent of transfusion within 14 days of Screening); Hemoglobin \geq 9.0 g/dL;
 - Renal function: Serum creatinine \leq 2.0 mg/dL or calculated creatinine clearance \geq 50 mL/min;
 - Hepatic function and enzymes: AST and ALT \leq 3.0 \times the upper normal limit (ULN) of institution's normal range; Bilirubin \leq 1.5 \times ULN. Subjects with Gilbert's Syndrome may have a Bilirubin > 1.5 \times ULN;
 - Coagulation: aPTT, PT must not exceed 1.2 \times ULN.
7. Female subjects must be surgically sterile, postmenopausal (for at least 1 year), or have negative results for a pregnancy test performed as follows:
 - At Screening on a serum sample obtained within 14 days prior to initial study drug administration, and
 - Prior to dosing on a urine sample obtained on Lead-in Day 1 if it has been > 7 days since obtaining the serum pregnancy test results.
8. All female subjects not surgically sterile or postmenopausal (for at least 1 year) and non-vasectomized male subjects must practice at least one of the following methods of birth control:
 - total abstinence from sexual intercourse (minimum one complete menstrual cycle);
 - a vasectomized partner;
 - hormonal contraceptives (oral, parenteral or transdermal) for at least 3 months prior to study drug administration;
 - double-barrier method (including condoms, contraceptive sponge, diaphragm or vaginal ring with spermicidal jellies or cream).

9. The subject must voluntarily sign and date an informed consent, approved by an Independent Ethics Committee (IEC)/Institutional Review Board (IRB), prior to the initiation of any screening or study-specific procedures.

5.2.4 Phase 2a Exclusion Criteria

A subject will not be eligible for study participation if he/she meets any of the following criteria:

1. The subject has a history or is clinically suspicious for cancer-related Central Nervous System (CNS) disease.
2. The subject has a recent history (within 1 year prior to first dose of study drug) of an underlying, predisposing condition of bleeding or currently exhibits signs of bleeding.
3. The subject has undergone an allogeneic or autologous stem cell transplant.
4. The subject has active peptic ulcer disease or other potentially hemorrhagic esophagitis/gastritis.
5. The subject has active immune thrombocytopenic purpura or a history of being refractory to platelet transfusions (within 1 year prior to the first dose of study drug).
6. The subject is currently receiving or requires anticoagulation therapy or any drugs or herbal supplements that affect platelet function, with the exception of low-dose anticoagulation medications that are used to maintain the patency of a central intravenous catheter.
7. The subject has received steroid therapy for anti-neoplastic intent within 7 days prior to the first dose of study drug with the exception of inhaled steroids for asthma, topical steroids or replacement/stress corticosteroids.
8. The subject has received aspirin within 7 days prior to the first dose of study drug.

9. The subject has received any anti-cancer therapy including chemotherapy, immunotherapy, radiotherapy, hormonal (with the exception of hormones for thyroid conditions or estrogen replacement therapy [ERT]), or any investigational therapy within 14 days prior to the first dose of study drug, or has not recovered to less than grade 2 clinically significant adverse effect(s)/toxicity(ies) of the previous therapy.
10. The subject has received a biologic within 30 days prior to the first dose of study drug.
11. The subject has consumed grapefruit or grapefruit products within 3 days prior to the first dose of study drug.
12. The subject has a significant history of cardiovascular disease (e.g., myocardial infarction [MI], thrombotic, or thromboembolic event in the last 6 months), renal, neurologic, psychiatric, endocrinologic, metabolic, immunologic, or hepatic disease that in the opinion of the investigator would adversely affect his/her participating in this study.
13. A female subject is pregnant or breast-feeding.
14. The subject has tested positive for HIV (due to potential drug-drug interactions between anti-retroviral medications and ABT-263, as well as anticipated ABT-263 mechanism based lymphopenia that may potentially increase the risk of opportunistic infections and potential drug-drug interactions with certain anti-infective agents).
15. The subject has a history of other active malignancies within the past 3 years prior to study entry, with the exception of:
 - adequately treated *in situ* carcinoma of the cervix uteri;
 - basal or squamous cell carcinoma of the skin;
 - previous malignancy confined and surgically resected with curative intent.

16. The subject exhibits evidence of other clinically significant uncontrolled condition(s) including, but not limited to:
- uncontrolled systemic infection (viral, bacterial, or fungal);
 - diagnosis of fever and neutropenia within one week prior to study drug administration.
17. The subject has received known CYP3A inhibitors (e.g., ketoconazole) within 7 days prior to first dose of study drug.

